6.1.3.1 Local Laboratory Assessments

Laboratory tests for screening should be performed within 10 days prior to the first dose of trial treatment. After cycle 1, pre-dose laboratory tests can be conducted up to 72 hours prior to dosing.

Laboratory test results must be reviewed by the investigator or qualified designee and found to be acceptable prior to administration of each dose of trial treatment. Unresolved abnormal laboratory tests that are drug-related AEs should be followed until resolution. Laboratory tests do not need to be repeated after the end of the treatment if laboratory values are within normal range.

6.1.3.2. Serum and Urine Pregnancy Tests

All women who are being considered for participation in the trial who are not surgically sterilized or postmenopausal, must be tested for pregnancy within 72 hours of each cycle of treatment and 30 days post the last dose of study treatment. If a urine test is positive or not evaluable a serum test will be required. Subjects must be excluded/discontinued from the study in the event of a positive or borderline-positive test result.

Table 10. Laboratory Tests

Hematology	Chemistry	Urinalysis	Other
Hematocrit	Albumin	Blood	Serum β-human chorionic gonadotropin†
Hemoglobin	Alkaline phosphatase	Glucose	(β-hCG)†
Platelet count	Alanine aminotransferase (ALT)	Protein	PT (INR)
WBC (total and differential)	Aspartate aminotransferase (AST)	Specific gravity	aPTT
Red Blood Cell Count	Lactate dehydrogenase (LDH)	Microscopic exam (If abnormal)	Total thriiodothyronine (T3)
Absolute Neutrophil Count	Carbon Dioxide ‡	results are noted	Free tyroxine (T4)
Absolute Lymphocyte Count	(CO ₂ or bicarbonate)	Urine pregnancy test †	Thyroid stimulating hormone (TSH)
	Uric Acid		PK
	Calcium		
	Chloride		Blood for correlative studies
	Glucose		
	Phosphorus		
	Potassium		
	Sodium		
	Magnesium		
	Total Bilirubin		
	Direct Bilirubin (If total bilirubin is elevated above the upper limit of normal)		
	Total protein		
	Blood Urea Nitrogen		

[†] Perform on women of childbearing potential only. If urine pregnancy results cannot be confirmed as negative, a serum pregnancy test will be required.

[‡] If considered standard of care in your region.

6.1.3.3. Pharmacokinetic/Pharmacodynamic Evaluations

6.1.3.3.1 Blood Collection for Serum Pembrolizumab

Sample collection, storage and shipment instructions for serum samples will be provided in the Laboratory Manual.

6.1.4 Other Procedures

6.1.4.1 Withdrawal/Discontinuation

When a subject discontinues/withdraws prior to trial completion, all applicable activities scheduled for the final trial visit should be performed at the time of discontinuation. Any adverse events which are present at the time of discontinuation/withdrawal should be followed in accordance with the safety requirements outlined in Section 6.2. - Assessing and Recording Adverse Events. Subjects who a) attain a CR or b) complete 24 months of treatment with pembrolizumab may discontinue treatment. After discontinuing treatment, these subjects should return to the site for a Safety Follow-up Visit and then proceed to the Follow-Up Period of the study as per the Trial Flow Sheet, unless they begin a new anti-cancer agent within 30 days of the last study treatment, in which case the end of treatment visit will be the day of the last dose of study therapy (section 5.0).

6.1.4.2 Blinding/Unblinding

This is an open label trial; there is no blinding for this trial.

6.1.5 Visit Requirements

Visit requirements are outlined in the Trial Flow Chart- Section 5.0. Specific procedure-related details are provided in section 6.0.

6.1.5.1 Screening

6.1.5.1.1 Screening Period

Approximately 28 days prior to treatment allocation, potential subjects will be evaluated to determine that they fulfill the entry requirements as set forth in Section 5.0. Screening procedures may be repeated.

Results of a test performed prior to the subject signing consent as part of routine clinical management are acceptable in lieu of a screening test if performed within the specified time frame. Screening procedures are to be completed within 28 days prior to the first dose of trial treatment except for the following:

. Laboratory tests and ECOG PS are to be performed within 10 days prior to the first dose of trial treatment. [SEP]

For women of reproductive potential, a serum pregnancy test will be performed within 72

hours prior to the first dose of trial treatment. A urine test may be considered if serum test is not appropriate. Subjects may be rescreened after initially failing to meet the inclusion/exclusion criteria. Results from assessments performed during the initial screening period are acceptable in lieu of repeat screening test if performed within the specified time frame and the inclusion/exclusion criteria is met. Subjects who are rescreened will retain their original screening number.

6.1.5.2 Treatment Period

Visit requirements are outlined in the Trial Flow Chart (Section 5.0). Specific procedure-related details are provided above in the Trial Procedures (Section 6.0).

6.1.5.3 Post-Treatment Visits

6.1.5.3.1. Safety Follow-Up Visit

The mandatory Safety Follow-Up Visit should be conducted approximately 30 days after the last dose of trial treatment or before the initiation of a new anti-cancer treatment, whichever comes first. All AEs that occur prior to the Safety Follow-Up Visit should be recorded. Subjects with an AE of Grade > 1 will be followed until the resolution of the AE to Grade 0-1 or until the beginning of a new anti-neoplastic therapy, whichever occurs first. SAEs that occur within 90 days of the end of treatment or before initiation of a new anti-cancer treatment should also be followed and recorded.

6.1.5.3.2. Follow-up Visits

Subjects who discontinue trial treatment for a reason other than CNS progression will move into the Follow-Up Phase and should be assessed every 6-9 weeks by radiologic imaging to monitor disease status. After 1 year, the imaging time point will occur every 9 weeks (\pm 7 days). Every effort should be made to collect information regarding disease status until the start of new anti-neoplastic therapy, disease progression, death, end of the study. Information regarding post-study anti-neoplastic treatment will be collected if new treatment is initiated.

6.1.5.3.3. Survival Follow-up

Once a subject experiences confirmed CNS progression or starts a new anti-cancer therapy, the subject moves into the survival follow-up phase and should be contacted by telephone every 12 weeks to assess for survival status until death, withdrawal of consent, or the end of the study, whichever occurs first.

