4.3.1.2 Dose Modification (Escalation/Titration/Other)

Adverse events (both non-serious and serious) associated with pembrolizumab exposure may represent an immunologic etiology. These adverse events may occur shortly after the first dose or several months after the last dose of treatment. Pembrolizumab must be withheld for drug-related toxicities and severe or life-threatening AEs as per Table 5 below. See Section 4.7 for supportive care guidelines, including use of corticosteroids.

Table 5. Dose Modification Guidelines for Drug-Related Adverse Events

Toxicity	Hold Treatment For Grade	Timing for Restarting Treatment	Treatment Discontinuation
Diarrhea/Colitis	2-3	Toxicity resolves to Grade 0-1	Toxicity does not resolve within 12 weeks of last dose or inability to reduce corticosteroid to 10 mg or less of prednisone or equivalent per day within 12 weeks
	4	Permanently discontinue	Permanently discontinue
AST, ALT, or Increased	2	Toxicity resolves to Grade 0-1	Toxicity does not resolve within 12 weeks of last dose
Bilirubin	3-4	Permanently discontinue (see exception below) ^a	Permanently discontinue
Type 1 diabetes mellitus (if new onset) or Hyperglycemia	T1DM or 3-4	Hold pembrolizumab for new onset Type 1 diabetes mellitus or Grade 3-4 hyperglycemia associated with evidence of beta cell failure	Resume pembrolizumab when patients are clinically and metabolically stable
Hypophysitis	2-4	Toxicity resolves to Grade 0-1. Therapy with pembrolizumab can be continued while endocrine replacement therapy is instituted	Toxicity does not resolve within 12 weeks of last dose or inability to reduce corticosteroid to 10 mg or less of prednisone or equivalent per day within 12 weeks
Hyperthyroidis m	3	Toxicity resolves to Grade 0-1	Toxicity does not resolve within 12 weeks of last dose or inability to reduce corticosteroid to 10 mg or less of prednisone or equivalent per day within 12 weeks
	4	Permanently discontinue	Permanently discontinue
Hypothyroidis m		Therapy with pembrolizumab can be continued while thyroid replacement therapy is instituted	Therapy with pembrolizumab can be continued while thyroid replacement therapy is instituted
Infusion	2 ^b	Toxicity resolves to Grade 0-1	Permanently discontinue if toxicity develops despite adequate premedication
Reaction	3-4	Permanently discontinue	Permanently discontinue

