5.0 TRIAL FLOW CHART

Table 7: Study Flow Chart

Trial Period:	Screenin g Phase	Treatment Cycles ^a						End of Treatment		Post-Treatment			
	Study Screening					showi	s 5+ on ng clin	nical b	enefit.				Survival
Treatment Cycle/Title:	(Visit 1)	1	2	3	4	5	6	7	8	Discon ⁹	Safety Follow-up	Follow Up Visits	Follow- Up
Scheduling Window (Days):	-28 to -1	± 3 ⁸	± 3	± 3	± 3	± 3	± 3	± 3	± 3	At time of discon	30 days post discon	Every 6-9 weeks post discon	Every 12 weeks
Administrative Procedures													
Informed Consent	X												
Inclusion/Exclusion Criteria	X												
Demographics and Medical History	X												
Prior and Concomitant Medication Review	X	X	X	X	X	X	X	X	X	X	X	X	
Post-study anticancer therapy status	X									X	X	X	
Survival Status													X
Clinical Procedures/Assessments													
Review Adverse Events	X	X	X	X	X	X	X	X	X	X	X	X	
Full Physical Examination	X									X			
Directed Physical Examination		X	X	X	X	X	X	X	X				
Vital Signs, Weight	X	X	X	X	X	X	X	X	X	X			
Oxygen saturation	X	X	X	X	X	X	X	X	X	X			
ECOG Performance Status	X	X	X	X	X	X	X	X	X	X			
Pembrolizumab Administration		X	X	X	X	X	X	X	X				
Laboratory Procedures/Assessments: anal	ysis perforr	ned by	LOCA	L labo	ratory								
Pregnancy Test – Urine or Serum β -HCG ¹	X	X	X	X	X	X	X	X	X	X	X		
PT/INR and aPTT	X												
CBC with Differential	X	X	X	X	X	X	X	X	X	X	X		

Trial Period:	Screenin g Phase	Treatment Cycles ^a							End of T	reatment	Post-Treatment		
	Study Screening					showi	s 5+ on ng clin continue	nical b	enefit.		G. C.	F 11 H	Survival
Treatment Cycle/Title:	(Visit 1)	1	2	3	4	5	6	7	8	Discon ⁹	Safety Follow-up	Follow Up Visits	Follow- Up
Scheduling Window (Days):	-28 to -1	± 3 ⁸	± 3	± 3	± 3	± 3	± 3	± 3	± 3	At time of discon	30 days post discon	Every 6-9 weeks post discon	Every 12 weeks
Comprehensive Serum Chemistry Panel	X	X	X	X	X	X	X	X	X	X	X		
Urinalysis	X												
TSH ²	X		X		X		X		X	X			
Hepatitis B, C, HIV	X												
Efficacy Measurements													
MRI Brain and Full-spine with contrast	X			X ³		X^3				X^3		X^4	
CT chest/abdomen/pelvis with contrast	X			X ³		X^3				X^3		X^4	
Tumor Biopsies/Archival Tissue Collection	ı/Correlativ	e Studi	ies Blo	od									
Archival Tissue Collection ⁵	X												
Blood collection for Genomics	X			X		X				X			
Blood collection for Immune correlates	X			X		X				X			
CSF sample acquisition ⁶	X			X		X ⁷				X^7			
CSF sample correlates	X			X		X^7				X^7			

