From the time of treatment allocation through 30 days following cessation of treatment, the investigator must report all adverse events. Such events will be recorded at each examination on the Adverse Event case report forms/worksheets. The reporting timeframe for adverse events meeting any serious criteria is described in section 7.2.3.1. The investigator will make every attempt to follow all subjects with non-serious adverse events for outcome.

Adverse events will not be collected for subjects during the pre-screening period (for determination of archival tissue status) as long as that subject has not undergone any protocol-specified procedure or intervention. If the subject requires a blood draw, fresh tumor biopsy etc., the subject is first required to provide consent to the main study and AEs will be captured according to guidelines for standard AE reporting.

6.2.1 Definition of an Overdose for This Protocol and Reporting of Overdose to the Sponsor and to Merck

For purposes of this trial, an overdose of pembrolizumab will be defined as any dose of 1,000 mg or greater (\geq 5 times the indicated dose). No specific information is available on the treatment of overdose of pembrolizumab. Appropriate supportive treatment should be provided if clinically indicated. In the event of overdose, the subject should be observed closely for signs of toxicity. Appropriate supportive treatment should be provided if clinically indicated.

If an adverse event(s) is associated with ("results from") the overdose of a Merck product, the adverse event(s) is reported as a serious adverse event, even if no other seriousness criteria are met.

If a dose of Merck's product meeting the protocol definition of overdose is taken without any associated clinical symptoms or abnormal laboratory results, the overdose is reported as a non-serious Event of Clinical Interest (ECI), using the terminology "accidental or intentional overdose without adverse effect."

All reports of overdose with and without an adverse event must be reported within 24 hours to the Sponsor and within 2 working days hours to Merck Global Safety. (Attn: Worldwide Product Safety; [contact])

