6.2.3 Immediate Reporting of Adverse Events to the Sponsor and to Merck

6.2.3.1 Serious Adverse Events

A serious adverse event is any adverse event occurring at any dose or during any use of Merck's product that:

- Results in death;
- Is life threatening;
- Results in persistent or significant disability/incapacity;
- Results in or prolongs an existing inpatient hospitalization;
- Is a congenital anomaly/birth defect;
- Is another important medical event

- Note: In addition to the above criteria, adverse events meeting either of the below criteria, although not serious per ICH definition, are reportable to the Merck in the same timeframe as SAEs to meet certain local requirements. Therefore, these events are considered serious by Merck for collection purposes.
 - Is a new cancer (that is not a condition of the study);
 - Is associated with an overdose.

Refer to Table 11 for additional details regarding each of the above criteria.

For the time period beginning when the consent form is signed until treatment allocation/registration, any serious adverse event, or follow up to a serious adverse event, including death due to any cause other than progression of the cancer under study that occurs to any subject must be reported within 24 hours to the Sponsor and within 2 working days to Merck Global Safety if it causes the subject to be excluded from the trial, or is the result of a protocol-specified intervention, including but not limited to washout or discontinuation of usual therapy, diet, placebo treatment or a procedure.

For the time period beginning at treatment allocation/registration through 90 days following cessation of treatment, or 30 days following cessation of treatment if the subject initiates new anticancer therapy, whichever is earlier, any serious adverse event, or follow up to a serious adverse event, including death due to any cause other than progression of the cancer under study (reference Table 11 for additional details), whether or not related to the Merck product, must be reported within 24 hours to the Sponsor and within 2 working days to Merck Global Safety.

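### Patients who stop for CNS progression and start no new therapy have no scheduled adverse event enquiry between the day-30 safety visit and day 90, so new SAEs in that period are found only passively

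*Combined protocol and SAP*

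**What the plan says.** **The duty.** Section 6.2.3.1 requires every SAE, related or not, to be reported "through 90 days following cessation of treatment, or 30 days following cessation of treatment if the subject initiates new anticancer therapy", whichever is earlier. Section 6.1.5.3.1 adds that "SAEs that occur within 90 days of the end of treatment or before initiation of a new anti-cancer treatment should also be followed". Sections 2.1 and 4.9 also state a 90-day period for each subject, and 6.2.4 gives events of clinical interest (ECIs) the same window. None of these sections makes an exception for CNS progression.

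**The contacts.** "The mandatory Safety Follow-Up Visit should be conducted approximately 30 days after the last dose of trial treatment", or before a new anti-cancer treatment if that comes first (6.1.5.3.1). After that the paths divide. "Subjects who discontinue trial treatment for a reason other than CNS progression will move into the Follow-Up Phase" and are seen every 6-9 weeks (6.1.5.3.2). After confirmed CNS progression, or once new therapy starts, "the subject moves into the survival follow-up phase and should be contacted by telephone every 12 weeks to assess for survival status" (6.1.5.3.3).

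**The flow chart.** In Table 7 (Section 5.0) the row "Review Adverse Events" is marked in 12 columns: screening, cycles 1 to 8, discontinuation, the 30-day visit and the follow-up visits. The thirteenth column, Survival Follow-Up, is blank in that row; its only entry is survival status. The row for post-study anti-cancer therapy is marked at screening, discontinuation, the 30-day visit and the follow-up visits, but not under Survival Follow-Up.

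**Late events.** On adverse events of possible immune origin, Section 4.3.1.2 says: "These adverse events may occur shortly after the first dose or several months after the last dose of treatment".

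**The concern.** The SAE duty is the same for everyone until day 90 or new therapy, but whether anyone is scheduled to ask about SAEs after day 30 depends on why the patient stopped. Those who stopped for other reasons are asked at follow-up visits. Those who stopped for CNS progression are telephoned about survival only.

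Safety is a secondary endpoint (4.1.5.1.2), and Section 7.2.5 lists SAEs among the events to be analysed. The plan works with 16 analysable patients (7.2.1), so one patient's event is 1/16, or 6.3 percentage points, of any per-patient rate. CNS progression is a mandatory reason to stop (4.9), so the group is unlikely to be empty. The events at stake are new, non-fatal SAEs in days 31-90, which is where the protocol itself says immune-related toxicity may still appear.

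A linked point is that the start of new anti-cancer therapy decides whether a patient's window is 30 or 90 days. The flow chart does not collect that fact at the calls these patients receive.

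**Working it through.** The plan states no figure on this point, so the check sets the SAE window against the contact schedule. Days count from end of treatment. As a simplification, last dose and discontinuation are treated as the same day.

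**Inputs.** SAE window: 90 days without new therapy (6.2.3.1). Safety visit: about day 30 (6.1.5.3.1). Follow-up visits: every 6-9 weeks (6.1.5.3.2). Survival calls: every 12 weeks (6.1.5.3.3).

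**1. Length of the interval after the last adverse event visit.** 90 - 30 = 60 days; 60/90 = 67% of the window.

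**2. When the first survival call falls.** Section 6.1.5.3.3 does not say from what date the 12 weeks run.
- From end of treatment: 12 x 7 = day 84, inside the window.
- From the safety visit: 30 + 84 = day 114, outside the window.

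On either count the call is specified for survival status only.

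**3. The same interval for the other groups.**

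| Group | Contacts with adverse event review after day 30 and by day 90 |
|---|---|
| Stopped for another reason, 6-weekly visits | days 42 and 84 (6 x 7, 12 x 7) |
| Stopped for another reason, 9-weekly visits | day 63 (9 x 7) |
| CNS progression, new therapy started | none needed under 6.2.3.1, which ends the window at day 30 |
| CNS progression, no new therapy | none scheduled, although the window runs to day 90 |

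The mismatch is confined to the last row. One qualification applies to the third. Section 6.1.5.3.1 ends the window when the new treatment starts, not at day 30. On that wording, a patient who starts new therapy between days 30 and 90 would have a shorter version of the same gap.

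**4. What still operates in the last row.** The reporting duty in 6.2.3.1 covers any SAE that becomes known, and related SAEs are reportable at any time. Section 6.1.5.3.1 keeps following an adverse event above Grade 1 that is already open, until it settles or new therapy begins. Deaths would surface through the calls, and cause of death is recorded (7.2.1, 7.2.5). That leaves new-onset, non-fatal SAEs and ECIs after day 30 that nobody volunteers.

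**5. Size of any under-count.** This would need the share of patients who stop for CNS progression without new therapy, and the SAE rate in days 31-90. The documents give neither, so no figure can be computed.

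**The case against.** The strongest answer is that a blank cell in a flow chart does not cancel a written duty. Section 6.1 says Table 7 only summarises the procedures and allows unscheduled ones. Section 2.1 lists 90-day monitoring and telephone follow-up for survival as separate activities, so the call need not be the vehicle for SAE collection. Sections 6.1.1.6.3 and 6.1.2.6 require review of all new anti-cancer therapy after the last dose, whatever the reason for stopping. All of this stands. What it does not supply is a contact at which somebody asks: the duties are stated, and after day 30 no scheduled contact carries them out for this group.

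Several stronger readings are tempting, and the documents do not support them:

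- **That nothing collects SAEs after day 30.** Sections 4.9, 6.1.5.3.1 and 6.2.3.1 require collection to day 90. What is missing is the scheduled prompt.
- **That SAE recording is tied to visits.** Section 6.2 says "Such events will be recorded at each examination on the Adverse Event case report forms/worksheets", but this refers to the preceding sentence, on all adverse events through 30 days. Serious events are sent to a separate section.
- **That late toxicity will be under-counted, or the safety endpoint biased low.** Passive ascertainment makes this possible, but no document figure shows that it will happen or how far. Section 4.1.5.1.2 also defines the safety endpoint by treatment-related toxicity above a grade threshold, not by an all-cause SAE rate to day 90.
- **That 67% of the safety data is lost.** Contacts collect retrospectively, so days between contacts are not lost days. On a 9-weekly schedule the other patients also have only one contact between days 30 and 90.

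**Conclusion.** The point holds in a limited form. For patients who stop for CNS progression and start no new anti-cancer therapy, SAE and ECI collection to day 90 is required, but no contact after the day-30 visit is scheduled to ask about adverse events. Ascertainment of new non-fatal SAEs in days 31-90 is passive for them and active for patients in the follow-up phase. Patients whose window ends at day 30 because of new therapy are not affected.

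The consequence is a risk of under-counting late immune-related events, of unknown size. The 60 days measure the interval without a scheduled question; they do not measure lost events. The 6.3 points per patient at N = 16 show only how much one event weighs. The conclusion rests on reading Table 7 and 6.1.5.3.3 as the schedule that sites will follow. The primary endpoint is untouched. This is a gap worth closing because it is cheap to close.

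**What to change.** In Table 7 and Section 6.1.5.3.3, for patients still inside the 90-day window:

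- Time the first survival call at about day 90 after end of treatment, and state that anchor, since the section now gives none.
- Have that call ask about SAEs and ECIs, hospitalisations, and any new anti-cancer therapy with its start date, since the safety visit.
- Mark adverse event review and post-study anti-cancer therapy under Survival Follow-Up for that contact, and add the items to the case report form.

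Later calls stay as planned. The change concerns data collection only.

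The cost is one planned call re-timed, with a few added questions and the matching flow chart and form wording. The call moves 6 days later if the 12 weeks were meant to run from end of treatment (90 - 84), or 24 days earlier if from the safety visit (114 - 90). No visit is added. The downside is that SAE information by telephone, recalled over up to 60 days, is less complete than at a visit.
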